Rationale for Study	
30-40% of patients who undergo RP with curative intent for their localized prostate cancer experience relapse of their disease. Thus, improved therapeutic approaches are needed in this patient population. Enhancing the patient's anti-tumor immune response prior to surgery may improve long-term outcomes following RP.
 
Tumor-infiltrating B cells are increased in prostate cancer tissue, and high intra-tumoral density of B cells correlate with higher stage of disease and greater potential for recurrence or progression (Woo JR et al, 2014). Unpublished data from UCSF's laboratory have shown that T cells within the prostate that are associated with B cell aggregates lack T cell activation markers. Recently, preclinical studies showed that ibrutinib, a potent inhibitor of Bruton's tyrosine kinase (BTK) but also an inhibitor of interleukin-2 inducible T-cell kinase (ITK) enhances T-cell mediated antitumor immunity when combined with PD-L1 blockade (Sagiv-Barfi I et al, 2015).
 
Btk has also been found to be overexpressed in prostate cancer cells, which correlates with cancer grade, and the knockdown of Btk expression inhibits the growth of prostate cancer cells in vitro (Guo W et al, 2014). Therefore, inhibition of Btk may also have direct anti-tumor activity in prostate cancer. In this study, the immunomodulatory and cytotoxic effects of ibrutinib will be studied in patients with localized prostate cancer in the neoadjuvant setting.

Primary Objective	
• To assess safety in patients with localized prostate cancer.• To characterize B and T cell infiltration within prostate tissue of men with localized prostate cancer treated with neoadjuvant ibrutinib, and to compare B and T cell infiltration to a reference population of untreated patients who underwent RP.
Secondary Objectives	
• To characterize changes in the frequency and number of circulating B and T cells induced by neoadjuvant ibrutinib in patients with localized prostate cancer.• To determine the cytotoxic effect and clinical benefit (pathologic T0 at time of RP) of neoadjuvant ibrutinib in men with localized prostate cancer.
Exploratory Objectives	
• To examine Btk expression in prostate tumor cells and tumor-infiltrating B cells.• To determine the impact of neoadjuvant ibrutinib on PD-L1 expression in prostate cancer cells and tumor-infiltrating lymphocytes (TILs).• To determine the effects of neoadjuvant ibrutinib on T and B cell repertoire within the tumor and blood.

Study Design	
This is a phase 2 study of neoadjuvant ibrutinib in men with localized prostate cancer undergoing RP as their initial locally directed therapy with curative intent. In the safety lead-in phase, a cohort of 6 patients will be treated with ibrutinib 840 mg/d x 4 weeks to assess safety and adverse events (AEs). If no more than 2 out of 6 patients experience dose limiting toxicities (DLT), the study will continue accruing. DLTs will be assessed during the safety lead-in phase only, during treatment with ibrutinib and the period prior to RP. To assess the immune response following neoadjuvant treatment, tissue from RP specimen will be compared to tissue from core biopsy specimen obtained prior to treatment, with each subject serving as his own control. Immune infiltration will also be compared to a reference cohort of 12 patients who had undergone RP, matched to the study population using the UCSF CAPRA-S score.

Number of patients	
Three patients were enrolled at UCSF in an 840 mg/d x 2 weeks cohort; no DLTs occurred. At WUSM, a safety lead-in of 6 patients will be accrued at the 840 mg/d x 4 week dose level. In the event that no DLTs are encountered, an additional 18 patients will be enrolled for a total of 24 patients at the 840 mg/d x 4 week dose level. A full safety assessment will be carried out after the first 10 patients have completed the phase 2 study (6 in the safety lead-in + 4), and accrual will be suspended if 3 or more of these 10 patients experience grade 3 or 4 treatment-related toxicity.
 
If RP is delayed over 12 days after the last dose of ibrutinib therapy (i.e. from scheduling delay of RP), a replacement patient will be accrued. The maximum number of allowed replacement patients is 4 (see Section 12.4).

Duration of Therapy	All patients will receive ibrutinib for 4 weeks prior to RP. RP will be performed 7 to 12 days after the last dose of ibrutinib.
Duration of Follow up	All patients will be followed for 4 weeks after RP.
Duration of study	The study will conclude when the last patient has completed his 4-week follow-up after RP. The anticipated duration of study is 18-24 months. All treatment related adverse events will be followed until resolution or stabilization to grade ≤2 .
Study Drugs	
Ibrutinib, also known as PCI-32765 and marketed under the name Imbruvica, is a small molecule irreversible Btk inhibitor that has shown clinical efficacy in B cell malignancies by blocking BCR signaling. Btk inhibitors may prove to be efficacious for other cancers where B cells and BTK signaling contribute necessary mechanisms for tumor growth, including immunomodulatory mechanisms. The dose of 840 mg x 4 weeks has been established as safe in solid tumors.
 
The dose level for the phase 2 study is 840 mg/d x 4 weeks. In the event that DLTs are encountered in 2 or more of the initial 6 patients, dose escalation with cohort of 6 per dose level are as follows:
 
Level -1: 840mg x 2 weeks Level -2: 560mg x 2 weeks

Safety Assessments	
Safety will be assessed by reviewing adverse events (AEs), laboratory evaluations, and by physical examination. The NCI CTCAE v4.03 will be used. All AEs and serious AEs (SAEs) that occur on study drug or within 30 days after the last dose of study drug, will be recorded on case report forms (CRFs) from enrollment through 4 weeks post-surgery.
 
The study will be halted if 4 of the first 4, or 5 of the first 9, or 6 of the first 14, or 7 of the first 18, or 8 of the first 23, or if the 9th non-hematological toxicity is observed before the last patient has completed the trial. Accrual will be stopped and the event will be reviewed by the Data Safety and Monitoring Board if a grade 5 non-hematological toxicity is observed.

Efficacy Assessments	
For the primary endpoints, toxicities will be assessed according to NCI CTCAE v.4.03 and changes in B cell infiltration within prostate tissue between core biopsy and RP specimen will be quantified using immunohistochemistry (IHC). A positive result is considered to be ≥ 2 fold decrease in the number of B cell infiltration.
 
For the secondary endpoints, immune subsets including B and T cells will be analyzed in the blood via flow cytometry, and in the core biopsy and RP specimens via IHC.

Unique Aspects of this Study	
This is the first study to evaluate the safety of ibrutinib and its effect on B cell infiltration in the neoadjuvant setting for patients with localized prostate cancer. The secondary and exploratory objectives will enhance our understanding of the immunomodulatory and cytotoxic effects of Btk inhibition in prostate cancer. Findings may justify further exploration of ibrutinib in prostate cancer, including combinational therapy in advanced prostate cancer.

List of Abbreviations

5-HT	5-hydroxytryptamine (serotonin)
ADL	activity of daily living
ADT	androgen deprivation therapy
AE	adverse event
ALP	alkaline phosphatase
ALT	alanine aminotransferase
ANC	absolute neutrophil count
AST	aspartate aminotransferase
ATC	Anatomical Therapeutic Chemical (Classification System)
AUC	area under the curve
B-CLL	B-cell chronic lymphocytic leukemia
BCR	B-cell receptor
Breg	B regulatory cells
BSA	body surface area
BTK	Bruton's tyrosine kinase
BUN	blood urea nitrogen
CAPRA	Cancer of the Prostate Risk Assessment
CBC	complete blood cell (count)
CHR	Committee on Human Research (UCSF IRB)
CpG	cytosine-phosphate-guanine
CNS	central nervous system
CR	complete response
CRC	Clinical Research Coordinator
CrCl	creatinine clearance
CRF	case report form
CSF	cerebral spinal fluid
CT	computerized tomography
CTCAE	Common Terminology Criteria for Adverse Events
CTEP	Cancer Therapy Evaluation Program
CTL	cytotoxic T lymphocyte
CTLA-4	cytotoxic T-lymphocyte-associated protein 4
CTMS	Clinical Trial Management System
CYP	cytochrome P450
DFS	disease-free survival
DL	dose level
DLBCL	diffuse large B-cell lymphoma
DLT	dose limiting toxicity
D2	dopamine receptor D2
DSMC	Data and Safety Monitoring Committee
DSMP	Data and Safety Monitoring Plan
EC ₅₀	median effective concentration
ECG	Electrocardiogram
ECOG	Eastern Cooperative Oncology Group
FCBP	female of childbearing potential
FDA	Food and Drug Administration
FIH	first-in-human
FL	follicular lymphoma
GCP	Good Clinical Practice
g/dL	gram per deciliter
Hb	Hemoglobin
HBcAb	Hepatitis B core antibody
HBeAg	Hepatitis B "e" antigen
HBsAb	Hepatitis B surface antibody
HBsAg	Hepatitis B surface antigen

List of Abbreviations

HBV	hepatitis B virus
HCT	Hematocrit
HCV	hepatitis C virus
HDFCCC	Helen Diller Family Comprehensive Cancer Center
HED	human equivalent dose
HGB	Hemoglobin
HIV	human immunodeficiency virus
IB	investigator's brochure
IC ₅₀	concentration that inhibits a process by 50%
ICH	International Conference on Harmonization
IHC	immunohistochemistry
IND	investigational new drug application
INR	international normalized ratio
IP	investigational product
IRB	Institutional Review Board
iwCLL	International Workshop on Chronic Lymphocytic Leukemia
IV	intravenous
LDH	lactate dehydrogenase
LFT	liver function test
LHRH	luteinizing hormone releasing hormone
LLN	lower limit of normal
LMWH	low molecular weight heparin
MCL	Mantle cell lymphoma
MedDRA	Medical Dictionary for Regulatory Activities
min	Minute
mL	milliliter
MM	multiple myeloma
MRI	magnetic resonance imaging
MTD	maximum tolerated dose
MZL	marginal zone lymphoma
NCI	National Cancer Institute
NHL	non-Hodgkin's lymphoma
nM	nanomolar
NOAEL	no-observed-adverse-effect level
NSCLC	non-small cell lung carcinoma
ORR	overall response rate
OTC	over the counter
PBMC	peripheral blood mononuclear cells
PD	disease progression
PD-1	programmed cell death protein 1
PD-L1	programmed death-ligand 1
PK	pharmacokinetics
Plt	platelet (count)
PML	progressive multifocal encephalopathy
PO	Per os (by mouth, orally)
PR	partial response
RP	radical prostatectomy
PRC	Protocol Review Committee (UCSF)
PSA	prostate specific antigen
pT0	pathologic complete response
PT	prothrombin time
PTT	partial thromboplastin time
QOL	Quality of Life
QTc	QT interval corrected for heart rate
RBC	red blood cell (count)

List of Abbreviations

SAE	serious adverse events
SD	stable disease
SD	standard deviation
SGOT	serum glutamic oxaloacetic transaminase
SGPT	serum glutamic pyruvic transaminase
SIP-T	sipuleucel-T
SLL	small lymphocytic lymphoma
SJS	Stevens-Johnson Syndrome
$t_{1/2}$	half-life
TCR	T-cell receptor
TILs	tumor infiltrating lymphocytes
T_{max}	time to maximum concentration
TPC	Tissue Procurement Core
ULN	upper limit of normal
μL	microliter
WBC	white blood cell (count)
WM	Waldenstrom's macroglobulinemia

STATEMENT OF COMPLIANCE

The trial will be carried out in accordance with International Conference on Harmonisation Good Clinical Practice (ICH GCP) and the following:

- United States (US) Code of Federal Regulations (CFR) applicable to clinical studies (45 CFR Part 46, 21 CFR Part 50, 21 CFR Part 56, 21 CFR Part 312, and/or 21 CFR Part 812)

National Institutes of Health (NIH)-funded investigators and clinical trial site staff who are responsible for the conduct, management, or oversight of NIH-funded clinical trials have completed Human Subjects Protection and ICH GCP Training.

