1.4 Rationale for Study Design

This study will evaluate the immunologic and cytotoxic changes induced by ibrutinib in prostate tissues compared to pretreatment biopsies. Three patients were enrolled at the 840 mg/d x 2 weeks dose level at UCSF and no DLTs were seen. A safety lead-in consisting of 6 patients will be enrolled at the 840 mg/d x 4 weeks dose level to evaluate the safety and tolerability of ibrutinib administered for 4 weeks preoperatively in patients scheduled for RP. If fewer than 2 DLTs are seen, an additional 18 patients will be treated with ibrutinib at the 840 mg/d x 4 weeks dose level before undergoing RP.

The safety profile of ibrutinib is well established from multiple studies in subjects treated with single agent ibrutinib (1061 subjects with B cell malignancies, 143 healthy subjects). Ibrutinib is generally well tolerated, and treatment related adverse events are generally manageable. The rationale for studying ibrutinib at dose of 840mg is that the dose of ibrutinib required for activity in solid malignancies via immune modulation and/or direct cytotoxicity may be higher than 560mg, the dose currently approved for hematologic malignancies. In the phase 1 study of ibrutinib in relapsed or refractory B-cell NHL and B-cell CLL, MTD was not reached after dose escalation from 2.5mg/kg/day to 12.5mg/kg/day (Advani RH et al. J Clin Oncol 2012). The phase 1b/2 study of ibrutinib in relapsed/refractory CLL or small lymphocytic lymphoma showed similar efficacy and toxicity profiles of ibrutinib administered at 420mg and 840mg (Byrd JC, et al. N Engl J Med 2013). Recently, interim data from an open label phase 2 study of ibrutinib combined with dexamethasone in relapsed/refractory multiple myeloma showed manageable toxicities at a dose up to 840mg (Vij R et al. ASH 2014). We therefore believe that the dose of ibrutinib 840mg will be well tolerated in patients with localized prostate cancer.

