3 STUDY DESIGN

3.1 Characteristics

This is a single center phase 2 open label study starting with a safety lead-in ibrutinib administered as neoadjuvant therapy in patients with localized prostate cancer. We believe that the dose of ibrutinib 840mg x 4 weeks will be well tolerated in patients with localized prostate cancer based on current trial data on ibrutinib but to ensure safety, we will start with a safety run-in. Previously at UCSF, 3 patients were enrolled to the 840 mg/d x 2 weeks dose level. No DLTs were observed. Beginning at WUSM, patients will be enrolled at the dose level of 840 mg/d x 4 weeks. If there are fewer than 2 DLTs, the Phase II dose expansion study will open and enroll up to an additional 18 patients to be treated with ibrutinib 840mg PO daily for 4 weeks.

If there are ≥ 2 DLTs in the safety lead-in, dosing will be de-escalated as follows:

- Level -1: 840 mg/d x 2 weeks, followed by de-escalation if ≥ 2 DLTs to Level -2
- Level -2: 560 mg/d x 2 weeks

In each enrolled patient, neoadjuvant ibrutinib therapy will be followed by radical prostatectomy (RP) performed 7 to 12 days after the last dose of ibrutinib. Pre-treatment and RP tissue will be evaluated for immunologic characterization, Btk expression and pathologic response. The proportion of patients achieving $\geq 50\%$ PSA decline will be assessed. Serum will also be obtained to characterize circulating immune response. All patients will be followed clinically for 4 weeks after RP to monitor for adverse events.

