6.1.2 Regimen Description

Study Drug	Premedication; precautions	Route	Schedule
Ibrutinib	No premedication required	Oral	Days 1-28

Ibrutinib is supplied in 140mg capsules. Patients in the safety lead-in will be treated at a dose of 840 mg PO daily x 4 weeks. If fewer than 2 DLTs are observed, patients will continue to be treated at that dose level. If ≥ 2 DLTs are observed, dose de-escalation is required. The first reduction will be to Level -1 (840 mg/d x 2 weeks) and the second reduction (if ≥ 2 DLTs are observed at Level -1) will be to Level -2 (560 mg/d x 2 weeks).

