12.5 Stopping Rules

If ≥ 2 patients experience DLTs during the safety lead-in, then the dose of ibrutinib will be reduced as follows:

- Level -1 840 mg/d x 2 weeks; if ≥ 2 of 6 DLTs are observed at Level -1, dosing will be de-escalated to Level -2
- Level -2 560 mg/d x 2 weeks

If ≥ 2 patients experience DLTs at Level -2, then the study will be terminated for lack of safety.

Toxicity is continuously monitored for all patients.

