12.5.1 Non-hematological Toxicity and plans for data and safety monitoring

Early stopping of the Phase II phase of the trial will be based on unacceptable non-hematological toxicity. Approximately less than 15% of patients are expected to

experience grade 3 and up toxicity and a non-hematological toxicity rate of 30% or more would definitely be unacceptable. Based on the sequential probability ratio test (SPRT) with 80% power and a 0.05 significance level, the study will be halted if 4 of the first 4, or 5 of the first 9, or 6 of the first 14, or 7 of the first 18, or 8 of the first 23, or if the 9th non-hematological toxicity is observed before the last patient has completed the trial. Accrual will be stopped and the event will be reviewed by the Data Safety and Monitoring Board if a grade 5 non-hematological toxicity is observed.

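### The Abstract's lead-in DLT thresholds conflict with the operative rule: one sentence continues accrual at exactly 2 of 6 patients, where Sections 3.1, 6.1.2 and 12.5 lower the dose

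*Combined protocol and SAP*

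**What the plan says.** The lead-in treats 6 patients at 840 mg daily for 4 weeks, and their DLTs decide whether 18 more are treated at that dose. The rule is stated in several places.

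- Abstract, Study Design: "If no more than 2 out of 6 patients experience dose limiting toxicities (DLT), the study will continue accruing".
- Abstract, Number of patients: the 18 further patients are described as following when there are no DLTs. Nothing is said there about 1 DLT.
- Abstract, Study Drugs: "In the event that DLTs are encountered in 2 or more of the initial 6 patients", the plan moves to Level -1 (840 mg for 2 weeks) and then Level -2 (560 mg for 2 weeks). The row calls this an escalation, although both levels are reductions.
- Section 1.4: "If fewer than 2 DLTs are seen, an additional 18 patients will be treated with ibrutinib" at the full 4-week regimen.
- Section 3.1: expansion opens below 2 DLTs. After a greater-than-or-equal sign the section continues "2 DLTs in the safety lead-in, dosing will be de-escalated as follows".
- Section 6.1.2: the dose is kept below 2 DLTs. At 2 or more, "DLTs are observed, dose de-escalation is required".
- Section 12.5: if 2 or more "patients experience DLTs during the safety lead-in, then the dose of ibrutinib will be reduced as follows", to Level -1 and then Level -2.

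**The concern.** A go/no-go dose rule should give one action for each possible result. Here a lead-in with exactly 2 of 6 affected patients falls on the continue side of one sentence and on the reduce side of five other statements (the Study Drugs row and Sections 1.4, 3.1, 6.1.2 and 12.5, where 1.4 withholds expansion rather than naming a reduction). A lead-in with exactly 1 of 6 continues under the Study Design row and falls below the Study Drugs trigger, but it is outside the condition in the Number of patients row.

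The next men treated are awaiting surgery with curative intent, and a drug-related delay of that surgery is itself a DLT under Section 6.1.4. If the Study Design sentence were followed after 2 of 6, at least 4 more men would receive the full regimen before the 10-patient safety assessment described in the Abstract.

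**Working it through.** **Step 1. Action by result.** The Study Design row is read as continuing at the lead-in dose.

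| Patients with a DLT (of 6) | Study Design row | Number of patients row | Study Drugs row; Sections 3.1, 6.1.2, 12.5 | Section 1.4 |
|---|---|---|---|---|
| 0 | continue | expand | no reduction | expand |
| 1 | continue | not covered | no reduction | expand |
| 2 | continue | not covered | reduce | do not expand |
| 3 or more | do not continue | not covered | reduce | do not expand |

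The table takes one DLT per affected patient. Sections 1.4, 3.1 and 6.1.2 count DLTs, while the Study Design row, the Study Drugs row and the first sentence of Section 12.5 count patients. Section 6.1.4 lists recurrence of the same grade 3 toxicity as a separate DLT item, so one man could contribute two. An event count would then de-escalate and a patient count would not.

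**Step 2. Inputs for the size.** The cohort is n = 6 (Section 3.2). The plan states no DLT rate and no operating characteristics for this rule, so there is no figure to reproduce. The rates p = 5%, 10%, 15%, 20% and 30% are assumptions. They are anchored loosely on Section 12.5.1: "Approximately less than 15% of patients are expected to" have grade 3 or higher toxicity, and "a non-hematological toxicity rate of 30% or more would definitely be unacceptable". Neither is a DLT rate.

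**Step 3. Formulas,** with X the number of patients with a DLT, binomial(6, p):

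- P(X = 0) = (1-p)^6
- P(X = 1) = 6p(1-p)^5
- P(X = 2) = 15p²(1-p)^4
- Study Design row continues: P(X ≤ 2)
- Section 12.5 rule continues: P(X ≤ 1)

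The gap between the last two is P(X = 2). For p = 0.30: P(X = 2) = 15 × 0.09 × 0.2401 = 0.324, P(X ≤ 1) = 0.1176 + 0.3025 = 0.420, and P(X ≤ 2) = 0.744.

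| Assumed p | P(X = 0) | P(X = 1) | P(X = 2) | Continue if ≤ 2 (Study Design) | Continue if < 2 (Section 12.5) |
|---|---|---|---|---|---|
| 5% | 73.5% | 23.2% | 3.1% | 99.8% | 96.7% |
| 10% | 53.1% | 35.4% | 9.8% | 98.4% | 88.6% |
| 15% | 37.7% | 39.9% | 17.6% | 95.3% | 77.6% |
| 20% | 26.2% | 39.3% | 24.6% | 90.1% | 65.5% |
| 30% | 11.8% | 30.3% | 32.4% | 74.4% | 42.0% |

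If the Number of patients row were read as a requirement, the P(X = 0) column would be the chance of expanding.

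**Step 4. Later checks after 2 of 6.** The 10-patient assessment suspends accrual at 3 or more of 10 with grade 3 or 4 treatment-related toxicity. Suppose both lead-in DLTs qualify, no other lead-in patient does, and the next 4 patients have the same rate p. Suspension then needs at least 1 of those 4, with probability 1-(1-p)^4. At the five rates this is 18.5%, 34.4%, 47.8%, 59.0% and 76.0%. For the sequential rule in Section 12.5.1, suppose the lead-in men are counted and both events are non-hematological. From 2 of 6, the boundary of 5 in 9 needs all of the next 3, and the boundary of 6 in 14 needs 4 of the next 8.

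**The case against.** The strongest reply is that the documents already resolve the conflict. Sections 3.1, 6.1.2 and 12.5 agree, Section 1.4 and the Abstract's own Study Drugs row support them, and a site working from the treatment and stopping sections would reduce the dose at 2. Individual patients are also protected. Under Section 6.2 a grade 4 treatment-related toxicity ends ibrutinib, and a grade 3 toxicity holds it until recovery and then halves the dose. The 10-patient assessment and the sequential rule follow. All of this stands and limits the harm. It does not remove the wrong sentence: I find no clause giving the body precedence over the Abstract, and the 10-patient assessment is itself found only in the Abstract.

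A second reply is that the Study Design sentence names no dose, and accrual also continues after de-escalation, in cohorts of 6. That is fair: reading it as continuing at the same dose is an inference. It is the natural one, because the sentence directly follows the description of the 840 mg, 4-week cohort and would otherwise set no threshold for the dose under test.

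A third reply is that the Number of patients row only describes one scenario. That may be so, but it then leaves 1 of 6 unaddressed where the reader would look for it.

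A reader might go further and infer that the trial has no usable de-escalation rule, or that men would in fact be overexposed. The documents do not support either: the operative sections give one consistent threshold. Nor is it right that every statement other than the Study Design sentence uses the cut-off of 2, since the Number of patients row does not.

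**Conclusion.** The point holds as an error in the current Abstract text. Two of its rows give lead-in conditions that do not match the rule in Sections 3.1, 6.1.2 and 12.5: the Study Design row is too permissive at exactly 2 of 6, and the Number of patients row covers only 0 DLTs. The first mismatch matters more, because it reverses the dose decision.

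The difference between the two rules is the chance of exactly 2 of 6: 17.6% at an assumed DLT rate of 15%, and between 3.1% and 32.4% over 5% to 30%. These figures assume independent patients with a common rate and at most one counted DLT each. They show how often the two rules would disagree, not how often harm would follow; that requires the Abstract sentence to be followed over the operative sections.

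**What to change.** In one amendment:

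1. Abstract, Study Design: *If fewer than 2 of 6 patients experience a DLT, the study will continue accruing at 840 mg/d x 4 weeks.*
2. Abstract, Number of patients: replace the condition of no DLTs with *fewer than 2 of 6 patients with a DLT*.
3. Abstract, Study Drugs: replace escalation with *de-escalation*.
4. State, following the first sentence of Section 12.5, that the unit is patients with at least one DLT, and carry this into Sections 1.4, 3.1 and 6.1.2.

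Items 1 to 3 are wording only and adopt the threshold that Section 12.5 already uses. Item 4 is a clarification of the rule and not only an edit: where one man has two DLTs and no one else has any, the event-count wording de-escalates and the patient-count wording does not. The investigators should confirm that choice. None of the four adds a visit, a test or a delay.
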